#### Financial aspect

Hypothesis: The extended triage intervention leads to an overall reduction in expenditures for the Health Insurance System (HIS) and the patient. The size of this reduction is determined by the presenting complaint (eMTS flowchart and urgency category), diagnosis, time of the day and patient characteristics.

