#### Research questions

- 9. What is the difference in average expenditures per patient for the Health Insurance System (HIS) and for the patient between intervention and control weekends for ambulatory patients presenting at the ED (and seen at the ED or at the GPC)?
- 10. What is the difference in average expenditures per patient for the HIS and for the patient between intervention and control weekends for different patients groups:
  - 10.1. Patients coded in the two least urgent categories (green and blue) presenting at the ED (and seen at the ED or at the GPC?
  - 10.2. Patients coded in the two most urgent categories (red and orange) presenting and treated at the ED?

- 11. For which type of medical treatment expenditures (consultation fees, medical imaging, clinical biology...) is there a difference between the control weekends and the intervention weekends (for patients described in 9 and 10)?
- 12. What are the determinants of treatment costs?

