Currently, the ED's software package sends all nomenclature codes except those for clinical biology and medical imaging to the financial department of the hospital, where the actual bills are made. The financial department draws up the bill, taking into account regulations; e.g. sometimes, regulation prohibits to bill two nomenclature codes simultaneously; the department then decides which one to charge.

To gain more insight in differences in expenditures for different patient groups (research questions 9 and 11), we need demographic and medical diagnostic information of the patient, which is not available on the invoices and is not accessible by the financial department of AZ Monica. We will therefore proceed as follows. We will make a table of all included patients with the following columns: time of arrival at the ED, year of birth, gender, ZIP-code and a new serial number created by us. We will transfer these data using encrypted messages. Because the financial department already has these data to make the invoices this does not raise any new privacy issues. The financial department will search for these included patients and deliver us a datasheet with all the information of the actual invoices linked to this new serial number but without any additional personal data. The nomenclature codes of the interventions performed at the ED can be transferred using iCAREdata.

If the reconstructed bills prove to be valid, research questions 10.1, 10.2. and 12 can be addressed with the variables collected in iCAREdata. For questions 10.1 and 10.2, we will calculate expenditures per patient (for the HIS and the patient) for urgency categories blue and green separately, and for urgency categories red and orange and compare them between the intervention and control weekends, using a t-test to test for statistical difference.

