For research question 12 we will perform a multivariate regression analysis, explaining the expenditures (dependent variable) with three sets of explanatory variables: general background characteristics of the patient (age, sex, insurance status), diagnostic information (urgency code, chosen eMTS flowchart) and system characteristics (occupancy rate ED, time of the day, triage nurse, intervention or control weekend). The coefficient for the dummy variable indicating an intervention weekend then gives the impact of the extended triage. It should confirm the effect found in 8. The inclusion of control variables, when estimating the impact in our regression, however reduces residual standard deviation and thus improves the precision

of the estimate. The coefficients on the other variables give a further insight in the additional determinants of expenditures. The regression analyses will be performed on the computer of the data manager using STATA.

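### The financial hypothesis says the size of the saving varies between patients, but apart from urgency groups no planned analysis estimates how it varies

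*Combined protocol and SAP*

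**What the plan says.** All references are to the combined protocol and SAP. Under Financial aspect, the hypothesis has two parts. The first is an overall fall in expenditure for the health insurance system and the patient. The second is "The size of this reduction is determined by the presenting complaint (eMTS flowchart and urgency category), diagnosis, time of the day and patient characteristics".

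The research questions that follow do not repeat the second part in full. Question 10 asks for intervention-control differences in the two least urgent and the two most urgent categories. Question 12 asks "What are the determinants of treatment costs".

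Under Methodology for the financial aspects, questions 10.1 and 10.2 are handled by t-tests within urgency groups: "we will calculate expenditures per patient (for the HIS and the patient) for urgency categories blue and green separately", and likewise for red and orange. The regression for question 12 uses "general background characteristics of the patient (age, sex, insurance status), diagnostic information (urgency code, chosen eMTS flowchart) and system characteristics", the last set being "occupancy rate ED, time of the day, triage nurse, intervention or control weekend". Its intervention term is read as follows: "The coefficient for the dummy variable indicating an intervention weekend then gives the impact of the extended triage". The covariates are there for precision ("The inclusion of control variables, when estimating the impact in our regression, however reduces residual standard deviation") and for description: "The coefficients on the other variables give a further insight in the additional determinants of expenditures". No interaction term, stratified regression or test of heterogeneity is mentioned.

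**The concern.** What determines the size of a saving is a question of effect modification. What determines the level of cost is a different question, and it is the one the regression is set up for. With a single intervention dummy, the model fits one common saving for all complaints, hours and patients.

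The design itself makes a common saving unlikely. The eMTS section allows allocation to primary care only from the two lowest urgency categories. The section A diagnostic Intervention says that, within those categories, some flowcharts send everyone to primary care and others no one. Any saving should therefore concentrate in certain combinations of urgency and flowchart, which is what the second part of the hypothesis sets out to learn.

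Two things are at stake. Flowchart, time of day and patient characteristics, all named as modifiers, get no estimate of their effect on the saving. And a covariate coefficient from the planned model could be taken as evidence of where extended triage saves money, which it cannot provide.

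**Working it through.** **1. Hypothesis against planned analyses**

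| Modifier named in the hypothesis | Saving estimated by level? | Savings compared between levels? |
|---|---|---|
| Urgency | Partly: blue and green, red and orange | No |
| Flowchart | No (cost regressor only) | No |
| Diagnosis | No (not listed as a regressor) | No |
| Time of day | No (cost regressor only) | No |
| Patient characteristics | No (cost regressors only) | No |

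The MTS has five categories. Question 10 takes the two lowest and the two highest, so 5 - 2 - 2 = 1, the middle (yellow) category, is left out.

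**2. What the additive model returns**

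The plan gives no expenditure figures, so the inputs are assumed: a saving of 40 euro by day and 0 at night, 60% of patients by day, and a true night excess in cost of 20 euro in control weekends. Let p be the share of patients in intervention weekends, with time of day balanced between weekend types. Regressing cost on the intervention dummy and a night indicator, without their product, gives:

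- dummy = -(0.6 x 40 + 0.4 x 0) = -24 euro, the correct average saving;
- night coefficient = true night excess + p x (day saving - night saving) = 20 + 40p.

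The share p follows from the allocation. The Design section can be read as one control to four intervention weekends (10.4 of 52, p = 0.80) or one in four (13 of 52, p = 0.75). The Introduction says one a month (12 of 52, p = 40/52 = 0.769). The night coefficient is then 20 + 32 = 52, 20 + 30 = 50, or 20 + 30.8 = 50.8 euro. A uniform saving of 24 euro with the same night excess would give 20.

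The coefficient therefore responds to the difference in saving but cannot be separated from the cost effect. At p = 0.769, these two situations give the same two coefficients:

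| | Night excess in control weekends | Saving by day / at night | Dummy | Night coefficient |
|---|---|---|---|---|
| A | 20 | 40 / 0 | -24 | 20 + 30.8 = 50.8 |
| B | 50.8 | 24 / 24 | -24 | 50.8 + 0 = 50.8 |

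**3. What an interaction adds**

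A simulation used 52 weekends of 154 patients, 12 of them control, with SD 60, a 50/50 modifier, no clustering and 200 runs (all but the 52 weekends and the monthly control assumed; 154 is 8000/52). The additive model's dummy was -9.9 when the saving was 10 in both groups and -10.1 when it was 20 in one and 0 in the other. With the product term, the interaction was about 0 in the first case (rejected in 3% of runs) and about -20 in the second (rejected in 100%).

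**4. Precision**

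Inputs: 8000 weekend attendances (Recruitment section), hence 8000/52 = 153.8 per weekend; two-sided 5% and 80% power (assumed). For a modifier with prevalence q, the minimum detectable difference in saving, in SDs of expenditure, is

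(1.96 + 0.84) x sqrt[(1/n_c + 1/n_i) x (1/q + 1/(1 - q))],

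where n_c and n_i are the numbers of control and intervention patients. With 12 control weekends, n_c = 1846 and n_i = 6154. For q = 0.5 this gives 2.80 x 0.0265 x 2 = 0.149. Across 10.4 to 13 control weekends:

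| q | Detectable difference (SD) |
|---|---|
| 0.50 | 0.145 to 0.157 |
| 0.20 | 0.181 to 0.196 |
| 0.05 | 0.332 to 0.359 |

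These figures are optimistic. They assume that weekend effects cancel within weekends, and the 8000 is before removal of excluded and admitted patients.

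**The case against.** Several points on the other side stand.

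- The regression is assigned to question 12, on determinants of cost, and main effects can answer that. A reader might infer that the model fails its own research question. It does not: the mismatch is between the hypothesis and the questions and analyses listed under it.
- Urgency is covered in part. Questions 10.1 and 10.2 estimate savings within urgency groups, and question 11 repeats this by type of expenditure. The methodology also says that demographic and diagnostic data are sought to learn about differences between patient groups. A reader might infer that the second part of the hypothesis gets no estimate at all. That is too strong: for urgency, what is missing is the middle category and a comparison between groups. The stated interest in patient groups comes with no method for the other modifiers.
- No model equation is given, so the absence of interactions is an inference. It is a fair one, because a single dummy coefficient is named as the impact, but the text does not exclude product terms.
- The plan already describes the other coefficients as determinants of expenditure, which reduces the risk of misreading. It does not remove it, because without interactions those coefficients also carry part of any difference in saving.
- The primary hypothesis is medical, and the financial work is presented as a first insight. This limits the weight of the point.

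**Conclusion.** The concern holds as a gap between a stated hypothesis and the analyses planned under it. Following the plan as written gives an average saving and savings in some urgency groups, but nothing on whether the saving differs by flowchart, time of day or patient characteristics. The average saving is not put in doubt by this point.

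A reader might go further and infer that the planned output would look much the same whether the saving is uniform or not, or that a night coefficient reflects cost alone. Neither follows. On the assumed figures the dummy is -24 euro either way, but the night coefficient moves by 30 to 32 euro. The sound conclusion is that this coefficient mixes a cost effect with the intervention share times the difference in saving, and cannot be read as either one alone.

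The euro amounts, SD, modifier prevalences and power settings are assumptions. The structural conclusion rests only on reading the described regression as additive.

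**What to change.** In the question 12 model, pre-specify interactions of the intervention indicator with a short list of modifiers recorded before the patient's destination is set: urgency at all five levels, grouped flowchart, time-of-day band, age and sex. Report the estimated saving per level with intervals that allow for clustering by weekend. Label these analyses exploratory and acknowledge multiplicity.

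In Methodology for the financial aspects, state that the covariate coefficients describe cost and do not show where extended triage saves money. In the hypothesis, drop diagnosis from the list of modifiers or treat it as descriptive, because it is recorded after the destination is set.

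The simpler alternative is to narrow the hypothesis to the average reduction.

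The cost is some wording and extra terms in a model that already contains these variables; no new data are needed. The downside is imprecision: with about 10 to 13 control weekends, broad modifiers may be informative, but single flowcharts probably will not be.

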#### Research questions

- 9. What is the difference in average expenditures per patient for the Health Insurance System (HIS) and for the patient between intervention and control weekends for ambulatory patients presenting at the ED (and seen at the ED or at the GPC)?
- 10. What is the difference in average expenditures per patient for the HIS and for the patient between intervention and control weekends for different patients groups:
  - 10.1. Patients coded in the two least urgent categories (green and blue) presenting at the ED (and seen at the ED or at the GPC?
  - 10.2. Patients coded in the two most urgent categories (red and orange) presenting and treated at the ED?

- 11. For which type of medical treatment expenditures (consultation fees, medical imaging, clinical biology...) is there a difference between the control weekends and the intervention weekends (for patients described in 9 and 10)?
- 12. What are the determinants of treatment costs?

#### Design of the clinical trial

#### A controlled longitudinal prospective intervention trial

To answer the above-mentioned research questions we need a longitudinal prospective intervention trial.

To allow definitive conclusions for our questions we need a control group. Historical controls will have too much confounding (not all data is available, the ED was organised in a different way, the GPC was unknown for many patients). Individually randomised controls are impossible from a practical point of view and because of contamination (patients will talk to each other and will not understand why some get a GPC advice and others not). Finally, randomisation by shift is not possible because they overlap in time. Therefore, randomisation is only possible by weekend. We will roll out one control weekend out of every four intervention weekends.

During a control weekend, all data registration and collection will be the same as during intervention weekends but we will not inform patients about their allocation advice. The emergency physician will see all patients deciding to stay at the ED, without influence of the triage advice. As in standard clinical care, patients will have the right to change their mind and go spontaneously to the GPC. Another difference is the communication to the patient: during intervention weekends, we will inform them about the intervention using leaflets and broadcasting in the waiting room of the ED. During control weekends, we will only inform about MTS-triage in general but no about the GPC. We will always mention the iCAREdata opting-out procedure.

#### **Inclusion and Exclusion**

We will systematically include all patients presenting at the ED during the weekend (the GPC is only open during the weekend starting from Friday 7 pm until Monday 6 am). By presentation at the ED we mean the patient is registered by the receptionist of the ED as a patient. Patients who just pass the ED to enter the hospital or who go directly to a medical department (e.g. obstetrics) are thus not included. The availability of a Belgian citizen national insurance number is the only inclusion criterion. This number is necessary to send the data needed for this study to the iCAREdata database. For the vast majority of patients this number is available. It will not be available for patients who present for the first time at the hospital and forgot all official documents. For patients without a Belgian identity (foreign citizens without Belgian health insurance, people without a legal status and babies less than one week old) the number is never available. The EDs own software allows us to calculate the number of excluded patients.

Patients arriving at the ED by an ambulance with a doctor or nurse (in Dutch called MUG or PIT) is the only exclusion criterion (these patients have already passed through a sort of triage). We estimate an exclusion rate of 15 patients per weekend.

#### Sample size

For this trial we consulted our subcontractor StatUA (core statistical facility of the University of Antwerp). If we only look at our primary research question ("What is the difference in the proportion of patients presenting at the ED and seen by the GP between intervention and control weekends"), straightforward power computations will tell that two weekends (one with, and one without intervention) are sufficient to provide empirical evidence of a statistically significant shift. However, as we want to know the determinants of this proportion and perform safety monitoring (including incident analysis), we need observations over a longer period of time. We do not know the impact size of the determinants that might act as confounders in this context. Because the eMTS is risk adverse, safety issues will be rare and a long study period is required

to identify and study possible safety issues. Finally, we expect nurses will need to build up experience with the eMTS before optimal results can be expected. For these reasons, we have chosen to include a large sample of patients by studying all weekends during one calendar year.

#### **Randomisation procedure**

We will assign the control weekends using randomisation software, taking into account possible confounders like bank holidays, school holidays, seasonal fluctuations...). We will not be able to blind the participants, the staff members nor the researchers. We will inform the staff about the nature of the upcoming weekend on Friday morning. Doing so, we aim to prevent anticipation of the staff (e.g. switching shifts or using less staff) and thus allocation bias.

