#### Aim of this project: we will advise you where to go

The aim of this project is to deliver the most appropriate care for patients presenting at the ED. To achieve this objective a triage nurse will assess all patients presenting at an ED and advise them on the most appropriate point of care: GPC or ED. Triage is 'the sorting out and classification of patients to determine priority of need'. Extended triage is triage combined with allocation to either ED or GPC, which is new in Flanders.

Many EDs in Flanders use the Manchester Triage system (MTS) in their regular care for triage within the ED, to sort patients according to the urgency of their presentation. We developed an extended MTS (eMTS) which foresees allocation to either ED or GPC. Scientific research is crucial to evaluate such triage systems before implementation is possible. Our study is a cluster-randomised trial. During one year, we will perform extended triage using the eMTS at one ED/GPC collaboration. Every month one weekend will serve as a control: the patient does not get an allocation advice.

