#### Recruitment strategy and expected dropout

Unlike most trials, we do not foresee any recruitment problems. In 2016, 8000 patients presented themselves during the weekend at the ED.

For each patient the study period is the time between presentation at the ED and discharge at either the ED or the GPC. This is a time span of only a few hours so the dropout rate will be negligible. Only when a patient leaves the site before consultation at the ED or GPC he or she is a dropout. This number of patients leaving the ED without being seen after triage (i.e. dropouts) is one of the safety indicators we will study. The number of these patients is currently less than five per weekend. We are able to measure this number using the triage reports through iCAREdata. Patients who leave without being seen before the triage-consultation will not be analysed.

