# Methodology for the medical aspect

The data necessary for this work package are part of a routine clinical report. We will use three types of these reports: triage-consultation reports, ED consultation reports and GPC consultation reports. We will collect these data using the iCAREdata database. This database can link our three types of clinical reports using an irreversibly coded national number. Due to data protection rules, the iCAREdata data manager will execute all queries and only aggregated results will be transferred to the researchers. For more complex statistical analysis, the data manager will transfer an analysis specific table or the analysis will be carried out on the computer of the data manager in cooperation between the researcher and the data-manager. A detailed data management plan is available. The correctness of a triage decision depends on the patient's situation:

- At the GPC (patients compliant to a GPC advice or non-compliant to an ED advice): the ratio of patients referred to an ED to the total number of patients coming from the ED of AZ Monica.
- At the ED (patients compliant to an ED advice or non-compliant to a GPC advice): the physician will answer the same question for all patients: "Should this patient better go to the GPC?". The correctness is defined as the ratio of the patients with a positive answer to this question to the total number of patients staying at the ED after triage.

The parameters of interest in questions 1 through 8 are (conditional) proportions, which calls for analysis by a non-linear model (e.g. binary logistic regression). The study design results in the creation of nested data, where patients are nested in weekends, and weekends are nested in (multiple) nurses. Appropriate analysis of such auto-correlated data requires a nonlinear mixed model. During the first months, data will be used to produce point-estimates of these proportions (e.g., patients seen by GP, correct triage decisions, all false positives, type 1 false positives, patients left without being seen, etc.). With increasing duration of the study, incoming data will be used to explain variability of these probabilities in terms of patient background characteristics, operating nurses/emergency physician, season, etc. Statistical assistance will be called for in order to conduct these analyses.

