# Methodology for the financial aspects

Resources are scarce and therefore it is essential to look at both outcome and resource use when introducing new treatments or treatment paths. This project incorporates both sides. We will use HIS expenditure data (including the share paid by the patient) to get a first insight in the changes in resource use due to the extended triage. Expenditures will be limited to the expenditures of the OOH consultation. In this way, we gain insight in the short-term impact of the new triage system on medical costs from the point of view of the patient and the HIS. For this aspect, we only focus on ambulatory patients (not admitted to the hospital). Although some inpatients can also present at the ED; admitted patients have far more complicated costs and they are not the focus of this project.

In our research we will make use of a cluster randomized trial to get an unbiased estimate of the difference in expenditures due to the extended triage. Randomization allows to measure the impact of the extended triage on average expenditures per patient (research question 9) or specific types of average expenditure per patient (research question 11) by comparing these average expenditures per patient between the intervention weekends and the control weekends. Information on the expenditures of consultations of the GPC are collected in the iCAREdata database. Expenditures generated by the ED are not yet routinely collected for research purposes, but billing data are available and these will be used. We will calculate the averages and use a t-test to test statistical significance. Medical bills also contain detailed information of the nomenclature codes (these are the codes used by the HIS, describing reimbursed care and reimbursement tariffs), performed during an ED visit. We will aggregate these interventions in similar groups such as consultation fees, medical imaging, clinical biology and so on. We will then compare these average expenditures per patient for the various aggregates between the intervention weekends and the control weekends (research question 10) and use a t-test for statistical significance.

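### No between-arm analysis commits to the calendar factors used to allocate control weekends: mixed-model intervals would be conservative, while the cost t-tests, which also ignore weekend clustering, would be too narrow

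*Combined protocol and SAP*

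**What the plan says.** **Allocation.** The weekend is the unit: "Therefore, randomisation is only possible by weekend". The Introduction (aim of the project) adds "Every month one weekend will serve as a control". Under Randomisation procedure the plan says "We will assign the control weekends using randomisation software, taking into account possible confounders like bank holidays, school holidays, seasonal fluctuations". It does not say whether this means strata, blocks or another constraint. The design section gives a different share, "We will roll out one control weekend out of every four intervention weekends", which does not match one per month exactly.

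**Medical analysis.** Methodology for the medical aspect recognises the clustering: "The study design results in the creation of nested data, where patients are nested in weekends", with weekends in turn linked to nurses. It therefore asks for a nonlinear mixed model. It gives no list of fixed effects for the model that estimates the intervention effect. Season is named among the variables that will explain variability once more data have come in, and research question 1.5 asks about season for the primary proportion. Bank and school holidays appear in no analysis.

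**Cost analysis.** Under Methodology for the financial aspects, mean costs per patient are compared between the two kinds of weekend: "We will calculate the averages and use a t-test to test statistical significance". The same test is planned for the cost types and the urgency groups. The regression for research question 12 adjusts for patient, diagnostic and system variables and includes an intervention dummy. It has no season, holiday or weekend term.

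**The concern.** When allocation is balanced on a factor that drives the outcome, the factor's variance drops out of the arm difference. An analysis that omits the factor still counts that variance in the standard error, so the standard error no longer describes the estimate. The plan itself treats the calendar factors as possible confounders, so it expects them to matter.

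The large primary shift that the sponsor expects may survive this. The smaller contrasts have less room: costs (questions 9 to 11), leaving without being seen (question 5) and workload (question 6), with only about 12 control weekends. For costs there is a second fault in the opposite direction. Patients within a weekend are treated as independent, although the weekend was randomised. The risk there is a false claim of a cost difference.

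**Working it through.** **The plan's own figure.** The Sample size section says that two weekends are enough for the primary question. It gives no alpha, power or proportions, so this cannot be reproduced. At two-sided 5%, with 139 independent patients per weekend, power is 0.81 for 2% v 10%, 0.80 for 5% v 15% and 0.27 for 2% v 5%. The statement is plausible for a large shift only.

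**Inputs from the plan**
- About 52 weekends ("studying all weekends during one calendar year").
- "In 2016, 8000 patients presented themselves during the weekend at the ED": 8000/52 = 154 per weekend. Less the estimated 15 exclusions, m = 139.
- Control weekends: 12 if monthly; 52/5 = 10.4 or 52/4 = 13 on the two readings of the design section.

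**Assumptions (not in the plan)**
- ICC b = 0.002 to 0.05.
- S, the share of between-weekend variance that the restriction removes from the arm difference, = 25 to 75%.

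**Variance per weekend mean (total variance set to 1)**
- True: b(1−S) + (1−b)/m
- Reported by a model with a weekend effect but no calendar factors: b + (1−b)/m
- Reported by a patient-level t-test: 1/m

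The number of weekends per arm cancels from the ratios, so the disagreement about the control share does not affect them.

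**Worked case, b = 0.01, S = 0.25**
- True: 0.0075 + 0.99/139 = 0.01462
- Weekend model without the factors: 0.01 + 0.00712 = 0.01712; ratio √(0.01712/0.01462) = 1.08
- Patient-level t-test: 1/139 = 0.00719; ratio √(0.00719/0.01462) = 0.70

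**Reported / true standard error at S = 25 / 50 / 75%**

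| ICC | Weekend model, factors omitted | Patient-level t-test |
|---|---|---|
| 0.002 | 1.03 / 1.06 / 1.09 | 0.91 / 0.94 / 0.97 |
| 0.01 | 1.08 / 1.19 / 1.33 | 0.70 / 0.77 / 0.86 |
| 0.05 | 1.13 / 1.34 / 1.71 | 0.40 / 0.48 / 0.61 |

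**When would the patient-level t-test be too wide?** Only if b(1−S) + (1−b)/m < 1/m, that is 1−S < 1/m = 1/139 = 0.7%. The calendar factors would have to explain more than 99.3% of the between-weekend variance.

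**Simulation under the null** (52 weekends in 13 blocks of four, one control per block, continuous outcome, 1,500 runs per setting). Type I error at ICC 0.01 and S = 25 / 50 / 75%:
- weekend-level test without the blocks: 3.5 / 2.1 / 0.9%
- patient-level t-test: 17.0 / 13.5 / 9.4%
- weekend-level test with the blocks: 4.6 / 5.4 / 4.7%

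Over all settings run, the block-adjusted analysis had type I error of 3.8 to 5.5% and standard-error ratios of 0.98 to 1.02.

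**Smaller weekends for costs.** The cost analysis covers ambulatory patients only, and the plan does not give their number. With an assumed m = 100, ICC 0.01 and S = 25%, the t-test ratio is √(0.0100/(0.0075 + 0.0099)) = 0.76. With S = 75% it is √(0.0100/(0.0025 + 0.0099)) = 0.90. The direction is the same and the size somewhat milder.

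**The case against.** - **Season is not ignored.** A reader might infer that the primary model leaves out all the allocation factors. The documents do not support that: season is named in the medical methods and in question 1.5, and the covariates of the effect model are unspecified. What stands is that nothing commits to season in the model that estimates the intervention effect, and that holidays are absent throughout.
- **The direction is not the same everywhere.** A reader might infer that the cost tests are conservative too. That would need t-tests on weekend means, which the plan does not mention; comparing mean costs per patient reads naturally as a patient-level test.
- **An adjusted cost estimate is planned.** The question 12 regression has an intervention dummy, and the plan says that covariates improve its precision. This is true, but its covariates include neither the calendar factors nor a weekend effect.
- **The restriction is not described.** The conservative direction assumes that allocation balances the factors. If the software only kept control weekends away from holidays, for example, holidays would be unbalanced, and leaving them out could bias the comparison. This is a further reason to state the mechanism.
- **Large effects need strong calendar factors.** At ICC 0.01 with 139 patients, between-weekend variance is 0.01/0.01712 = 58% of the variance of a weekend mean; the rest is patient-level noise that no calendar term removes. The upper ends of the ranges therefore need season and holidays to explain most of the variation between weekends. For leaving without being seen, currently fewer than five per weekend, noise should weigh more and the gain should be small.
- **Conservative is still valid.** For the mixed model the loss is precision, and the primary shift may be large enough to bear it. This limits the severity but does not remove the point.

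**Conclusion.** The concern holds as two faults of opposite sign. For a mixed model that keeps weekend clustering but omits the allocation factors, standard errors are about 3–9% too wide at ICC 0.002 and 8–33% at ICC 0.01, for S of 25–75%. For the cost t-tests read as patient-level, the missing clustering dominates: at ICC 0.01 the reported standard error is about 0.70–0.86 of the true one, and the type I error is about 9–17% instead of 5%.

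These sizes rest on the assumed ICC and S, on a restriction that balances the factors, and on a continuous outcome, so figures for the logistic model are approximate. The direction for the mixed model follows from the design. The direction for costs rests on the patient-level reading and on some residual variation between weekends. This should be corrected before analysis. It does not undermine the design or the primary comparison.

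**What to change.** 1. State the restriction used in randomisation (blocks, strata or constraints), and reconcile one control per month with the share given in the design section.
2. Include the allocation factors (month or quarter block, bank-holiday and school-holiday indicators) as fixed effects in the intervention-effect model for question 1 and in every other between-arm comparison.
3. Replace the cost t-tests with a model that has weekend as the cluster and the same terms.
4. Add these terms and weekend clustering to the question 12 regression.

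This is a change of SAP wording. Month and holiday status are known for every weekend, so no new data are needed. The cost is about 11 weekend-level degrees of freedom with month or 3 with quarter, plus one for each holiday indicator. Without them, a comparison of 52 weekend means has 52 − 2 = 50; month leaves 50 − 11 = 39 and quarter 50 − 3 = 47, before the holiday terms. Fixing the terms in advance also removes an analyst's choice in a trial where researchers are not blinded.
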